1.2.3.2 Pharmacodynamics

Cardiac electrophysiology studies were conducted in a QT/QTc trial that enrolled 48 health volunteers. In this study, BIC at doses 1.5 to 6 times recommended dose did not affect the QT/QTc interval and did not prolong the PR interval. TAF at the recommended dose or at a dose 5 times the recommended dose did not affect the QT/QTc interval and did not prolong the PR interval. The effect of FTC on the QT interval is not known. ([Biktarvy 2018](#))

In studies with healthy subjects, the mean change from baseline in serum creatinine with administration of BIC 75 mg (1.5 times the approved recommended dosage) once daily with food for 14 days was 0.1 mg per dL on Days 7 and 14 compared to placebo. BID did not have significant effect on the estimated creatinine clearance or on the actual glomerular filtration rate. ([Biktarvy 2018](#))

1.2.3.3 Pharmacokinetics

The pharmacokinetic (PK) properties of B/F/TAF components are summarized in **Table 1-1**. The multiple dose PK parameters of BIC, FTC, and TAF based on population pharmacokinetic analysis as well as a more complete PK description of the regimen and its components are found in the BIKTARVY U.S. package insert published by Gilead Sciences Inc. It should be noted that the pharmacokinetics of B/F/ TAF have not been evaluated in subjects coinfected with HBV.

Table 1-1: Pharmacokinetic Properties of BIC, FTC, and TAF

	BIC	FTC	TAF
Absorption			
t _{max} (hours)	2.0 - 4.0	1.5 - 2.0	0.5 - 2.0
Effect of high fat meal (relative to fasting)			
AUC ratio	1.24 (1.16, 1.33)	0.96 (0.93, 0.99)	1.63 (1.43, 1.85)
C _{max} ratio	1.13 (1.06, 1.20)	0.86 (0.78, 0.93)	0.92 (0.73, 1.14)
Distribution			
% bound to human plasma protein	>99%	<4%	~80%
Blood-to-plasma ratio	0.64	0.6	1.0
Elimination			
t _{1/2} (hours)	17.3 (14.8, 20.7)	10.4 (9.0)	0.51 (0.45, 0.62)
Metabolism			
Metabolic pathway(s)	CYP3A UGT1A1	Not significantly metabolized	Cathepsin A (PBMC) CES1 (hepatocytes)
Excretion			
Major route of elimination	Metabolism	Glomerular filtration and active tubular secretion	Metabolism
% of dose excreted in urine	35%	70%	<1%
% of dose excreted in feces	60.3%	13.7%	31.7%

The half-life of tenofovir diphosphate, the active metabolite of TAF, is between 150-180 hours within the hepatocytes. In vivo, TAF is hydrolyzed within cells to form tenofovir (major metabolite), which is phosphorylated to the active metabolite, tenofovir diphosphate. In vitro studies have shown that TAF is metabolized to tenofovir by cathepsin A in PBMCs and macrophages, and by carboxylesterase 1 (CES1) in hepatocytes.

1.2.4 Clinical Studies on Bictegravir/Emtricitabine/Tenofovir Alafenamide

Bictegravir/Emtricitabine/tenofovir alafenamide (B/F/TAF) has been clinically shown to be highly effective in the treatment of HIV-1 infection based upon two phase 3 treatment-naïve trials, the Study 1489 and Study 1490. In Study 1489 study ([Gallant J, et al. 2017](#)), N = 631, B/F/TAF demonstrated non-inferiority to DTG/ABC/3TC (VL ≤ 50 copies/mL at 48 weeks, B/F/TAF 92.4% vs. DTG/ABC/3TC 93.0%, p=0.78). No treatment emergent resistance developed in either treatment arm. This study excluded HIV-HBV coinfected patients. In Study 1490 ([Sax PE, et al. 2017](#)), N = 742, B/F/TAF demonstrated non-inferiority to DTG + TAF/FTC (VL ≤ 50 copies/mL at 48 weeks, BIC 89% vs DTG 93%, p=0.12). There were no treatment emergent resistance in either arm. In contrast to the previous study, HBV coinfection were allowed to be enrolled in Study 1490. Nevertheless, of the 320 patients in the study who received B/F/TAF, only eight (2%) subjects were coinfected with HBV ([Sax PE, et al. 2017](#)).

1.3 B/F/TAF in HIV-HBV Coinfection & Study Hypothesis

Though the safety and efficacy of B/F/TAF has been well established in the treatment of HIV-1 infection and TAF has been found to be as efficacious and durable as TDF in the treatment of HBV infection, there is limited data on the use of B/F/TAF in the HIV-HBV coinfected subpopulation. The 2 phase III registration studies (Treatment-naïve Study 1490 and switch Study 1878) that allowed HIV/HBV coinfected subjects to be enrolled had a total of only 16 coinfected subjects who received B/F/TAF ([Gallant J, et al. 2017](#), [Sax PE, et al. 2017](#)). In Study 1490, all eight coinfected participants who received B/F/TAF had HIV-1 RNA ≤50 copies/mL and HBV DNA <29 IU/mL at Week 48 ([Rockstroh JK et al. 2018](#)). Likewise, in Study 1878, all eight volunteers with HIV-HBV coinfection maintained suppression against both viruses ([Rockstroh JK et al. 2018](#)). Thus, there is a need for additional data to further validate the use of B/F/TAF as a mainstay regimen in the treatment of HIV-HBV coinfected people. This study will be conducted to obtain real-world data in a larger population to help address this need. The main hypothesis of this study is that fixed-dose combination (FDC) B/F/TAF is safe and efficacious in the treatment of adults coinfected with HIV-1 and HBV virus.

1.4 Risk and Benefit Assessments

1.4.1 Risk of using B/F/TAF (BIKTARVY®)

1.4.1.1 Adverse Events in Clinical Trials

The most common adverse events reported in at least 5% of subjects in those who have taken B/F/TAF are diarrhea, nausea, and headache. The proportion of subjects who discontinued treatment with B/F/TAF due to adverse events, regardless of severity was 1%. The majority (87%) of adverse events associated with B/F/TAF were Grade 1. **Table 1-2** displays the

frequency of adverse events greater than or equal to 2% in the two treatment naïve registry studies (Study 1489 and study 1490), attributed to study drug by the investigator. ([Biktarvy 2018](#))

Table 1-2: Adverse Reactions (All Grades) Reported in >2% of HIV Infected Adults with No Antiretroviral Treatment History Receiving B/F/TAF in Study 1489 or 1490 (Week 48 Analysis)

Adverse Reactions	Study 1489	Study 1490
	N=314	N=325
Diarrhea	6%	3%
Nausea	5%	3%
Headache	5%	4%
Fatigue	3%	2%
Abnormal dreams	3%	<1%
Dizziness	2%	2%
Insomnia	2%	2%

1.4.1.2 Pregnancy and Breastfeeding Risks

The prevalence of birth defects per 100 live births among HIV-1 infected women with a first trimester exposure to any ART is 2.7 (95% confidence interval (CI): 2.4-3.1), i.e. 255 outcomes with defects of 9,336 live births according to the Antiretroviral Pregnancy Registry, January 2018 interim report ([AP Registry 2018](#)). This prevalence of defects was not significantly different from those with an initial exposure during the 2nd and 3rd trimester, nor was it different from non-HIV population based pregnancy registries ([AP Registry 2018](#)). In the U.S. general population, the estimated background risk of major birth defects and miscarriage in clinically recognized pregnancies is 2–4% and 15–20%, respectively.

A pregnancy exposure registry (The Antiretroviral Pregnancy Registry or APR) is being used to monitors pregnancy outcomes in women exposed to B/F/TAF during pregnancy. Currently, there is insufficient human data on the use of B/F/TAF during pregnancy to inform of drug-associated risk of birth defects and miscarriage. Both BIC and TAF use in pregnant women have not been evaluated. There is a limited number of women with use of FTC use during pregnancy reported in the APR with prevalence rates not different from general population ([AP Registry 2018](#)). ([Biktarvy 2018](#))

In animal studies, there is no evidence of adverse reproductive developmental outcomes observed with any of the components of B/F/TAF at exposure that were either not maternally toxic (rabbits) or greater than (rats and mice) those in humans at the recommended human

dose (RHD). During organogenesis, systemic exposures to BIC were approximately 36 (rats) and 0.6 times (rabbits), to FTC were approximately 60 (mice) and 108 times (rabbits), and to TAF were approximately two (rats) and 78 times (rabbits) the exposure at the recommended human dose of B/F/TAF. ([Biktarvy 2018](#))

The Center for Disease Control and Prevention recommends that HIV-1 infected mothers in the U.S. not breastfeed their infants to avoid risking postnatal transmission of HIV-1 infection. Nevertheless, it is not known whether B/F/TAF or any of its components are present in human breast milk, affects human milk production, or has effects on the breastfeeding infant. ([Biktarvy 2018](#))

As the effects of B/F/TAF on an unborn baby or a nursing infant are not known, care must be taken to avoid pregnancy in female subjects or in female partners of male subjects during this study and following completion of study treatment (30 days after completion for women, 14 days after completion for men). Subjects will be excluded if they are pregnant, planning to become pregnant, or while breast-feeding.

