3.2.3.3 Week 48 Visit (\pm 4 weeks): End-of-Study Assessments

This describes the end-of-study assessments for all subjects including those who discontinue study prematurely.

- Obtain interval medical history.
- Conduct complete physical examination, including weight and vital signs [BP, R, HR, T].
- Collect concomitant medication information.
- Collect adverse event information.
- Evaluate Patient Diary and number of used and unused tablets.
- Plasma HIV-1 RNA.
- Plasma HBV DNA.
- Quantitative HBsAg level.
- CD4 cell count.
- HIV-1 genotype/phenotype, if HIV-1 RNA is \geq 500 copies/mL.
- HBV genotype and resistance assay, if HBV DNA is \geq 500 IU/mL.
- HBV profile.
- Complete blood count.
- Comprehensive metabolic panel.
- Coagulation tests.
- Urine pregnancy test for women of childbearing potential.
- FibroScan test (IHV only). This test may be done during the Visit, or within 2 weeks (before or after) the scheduled Week 48 visit.
- Blood for PAXgene RNA analysis.
- Blood for storage of plasma, serum, and PBMCs.

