3.2.6 End of Study

The end of study will be the last patient's last observation (or visit).

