6.3.3 Final Disposition of Clinical Supplies

At the end of the study, final study drug supply and accountability records will be reconciled as to drug shipped, drug consumed, and drug remaining. Any discrepancies noted will be documented.

Subject accountability for study drug will be ensured through subject interview (during visits), diaries, and study drug reconciliation at selected visits before dispensing drug supply for the next visit interval. At certain clinic visits, subjects will be asked to return any unused study drug to the study site. Final drug accountability reconciliation will be performed at the subject visit occurring at the end of therapy or at early discontinuation. Unused study drug will be destroyed.

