Adverse event information will be collected from the time subject signs the informed consent and until the end of the subject's study participation, i.e. Study Week 48 (end-of-study visit) or earlier if consent has been withdrawn. All AEs occurring after the subject has entered the study (that is, after the Informed Consent document is signed) must be recorded in the CRF. If the study drug is discontinued for a subject, study personnel must report and clearly document the circumstances and data leading to any such discontinuation, using designated CRFs. For AEs, the subject should be followed until the event resolves or stabilizes, with frequency of follow-up at the discretion of the investigator.

In case the investigator notices an unanticipated benefit to the subject, study personnel should enter "unexpected benefit" with the actual event term (for example, the complete actual term would be "unexpected benefit – sleeping longer").

Cases of pregnancy that occur during maternal or paternal exposures to study drug should be reported for tracking purposes. Data on fetal outcome and breastfeeding are collected for regulatory reporting and drug safety evaluation.

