APPENDIX A. SCHEDULE OF ACTIVITIES

Study Procedures	Screening (D-90 to -3)	Day 1	Study Week					
			4	8	12	24	36	48 ^g
Administrative Procedures								
Informed Consent	X							
Inclusion/Exclusion Criteria	X	X						
Complete Medical History	X							
Interval Medical History		X	X	X	X	X	X	X
Administer 1st Dose of Study Drug		X						
Study Drug and Diary Dispensation		X	X	X	X	X	X	
Study Drug Accountability			X	X	X	X	X	X
Clinical Procedures/Assessments								
Complete Physical Exam	X	X						X
Targeted Physical Exam, if needed			X	X	X	X	X	
Concomitant medication	X	X	X	X	X	X	X	X
Adverse event		X	X	X	X	X	X	X
Height	X							
Vital Signs (T, P, R, BP) and Wt	X	X	X	X	X	X	X	X
12-lead ECG	X							
Clinical Laboratory Tests								
Plasma HIV-1 RNA	X ^a	X	X	X	X	X	X	X
Plasma HBV DNA	X ^a	X	X	X	X	X	X	X
Quantitative HBsAg level	X ^a	X	X	X	X	X	X	X
CD4 Cell Count	X ^a	X			X	X	X	X
HBsAg/HBcAb/HBsAb/HBeAg/HBeAb	X ^a					X		X
HIV-1 Genotype/Phenotype ^b		X						X
HBV Resistance Assay ^c		X						X
HBV Genotype ^c		X						
HCV serology	X ^a							
HDV serology	X ^a							
CBC	X ^a	X	X	X	X	X	X	X
CMP	X ^a	X	X	X	X	X	X	X
Coagulation Tests (PT/PTT)	X ^a							X
Fibroscan (IHV only)		X ^e				X ^f		X ^f
Urinalysis	X ^a							
Urine pregnancy test (if WOCP ^d)		X	X	X	X	X	X	X
Serum pregnancy test (if WOCP ^d)	X							
Research Laboratory Tests								
PAXgene RNA Assay		X			X	X	X	X
PAXgene DNA Assay		X						
PBMC Storage		X	X	X	X	X	X	X
Plasma Storage		X	X	X	X	X	X	X
Serum Storage		X	X	X	X	X	X	X

[figure not shown]
Legend:

- ^a May use outside labs if within 90 days.
- ^b If HIV-1 RNA is ≥ 500 copies/mL
- ^c If HBV DNA is ≥ 500 IU/mL
- ^d Woman of childbearing potential
- ^e Fibroscan at Baseline (Day 1) may be conducted within 30 days prior to Day 1 Visit.
- ^f Fibroscan at Week 24 and Week 48, may be conducted 2 weeks before or after the Study Visit.
- ^g Week 48 (End of Study) Visit procedures will be used for Early Termination/Subject Withdrawal Visits.

[figure not shown]

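### The 30-day (women) and 14-day (men) pregnancy-avoidance period after treatment in Section 1.4.1.2 is missing from the contraception rules in criteria 7 and 8 and Appendix F

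*Combined protocol and SAP*

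**What the plan says.** Section 1.4.1.2 gives the reason for the precaution: the effects of B/F/TAF on an unborn or nursing child are unknown. It requires care to avoid pregnancy, in female subjects and in female partners of male subjects, during the study and for a stated time after treatment: "30 days after completion for women, 14 days after completion for men".

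The operative rules are elsewhere, and none of them mentions a period after treatment:

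- Inclusion criterion 7 (synopsis and Section 5.2) asks women of childbearing potential for contraception from screening for as long as the study lasts.
- Inclusion criterion 8 asks men for abstinence or condoms for the study period.
- Appendix F ends the female requirement at end of study. The male requirement covers treatment and then also runs to end of study.

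End of study is used in two senses. Section 3.2.6 defines it for the trial: "The end of study will be the last patient's last observation (or visit)". Section 7.1.1 uses it for the individual, whose participation ends at "Study Week 48 (end-of-study visit) or earlier if consent has been withdrawn". The heading of Section 3.2.3.3 and the Appendix A legend ("Week 48 (End of Study) Visit procedures will be used for Early Termination/Subject Withdrawal Visits") also attach it to the subject's Week 48 visit.

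**The concern.** Sites have two different stopping points for the same precaution. The one that subjects agree to at entry is the one without the post-treatment period. A site that follows Section 5.2 and Appendix F to the letter can let a completer stop contraception earlier than Section 1.4.1.2 asks. On the trial-level meaning of end of study, a subject's stopping date depends on when someone else finishes, so nobody can tell the subject that date in advance.

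What is at stake is participant protection and one clear rule. It is not a statistical matter: no endpoint, analysis or sample-size figure depends on it.

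**Working it through.** There is no plan figure to reproduce. The check compares the required days with the days covered.

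**Inputs**

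- Required after last dose: 30 days (women), 14 days (men), from Section 1.4.1.2.
- Treatment lasts 48 weeks (Section 3.1): 48 × 7 = Day 336.
- Week 48 visit window is ±4 weeks (Section 3.2.3.3): 336 − 28 = Day 308 to 336 + 28 = Day 364.
- No visit is scheduled after Week 48 (Appendix A).
- Planned accrual is 12 months (synopsis).

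**Formulas**

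- Cover = (day contraception may stop) − (day of last dose).
- Shortfall = max(0, required days − cover).

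**Reading 1: end of study is the subject's own Week 48 visit**

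| Last dose | Visit | Cover | Women short | Men short |
|---|---|---|---|---|
| Day of visit | any | 0 | 30 | 14 |
| Day 336 | Day 350 | 14 | 16 | 0 |
| Day 336 | Day 364 | 28 | 2 | 0 |

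With a last dose on Day 336, women would need a visit on Day 336 + 30 = 366, which is 2 days beyond the window.

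The first row is realistic for a completer. Section 6.3.3 says "Final drug accountability reconciliation will be performed at the subject visit occurring at the end of therapy or at early discontinuation", which places the end of therapy at a visit. The Week 36 visit dispenses a 90-day supply (Section 3.2.3.2). From nominal Day 36 × 7 = 252 this lasts to about Day 252 + 90 = 342, past Day 336.

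**Reading 2: end of study is the last patient's last visit**

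| Subject finishes before that date by | Women short | Men short |
|---|---|---|
| 0 days | 30 | 14 |
| 7 days | 23 | 7 |
| 14 days | 16 | 0 |
| 30 days | 0 | 0 |

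If the first and last completers enrol 12 months apart, the first is bound for about 365 days and the last for 0.

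**Other provisions that might close the gap**

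- Appendix F calls for a pregnancy test once relevant drug exposure has ended. It sets no contraception period, and the last scheduled test is at Week 48.
- Section 7.1.1 says "Cases of pregnancy that occur during maternal or paternal exposures to study drug should be reported for tracking purposes". It gives no number of days and does not extend contraception.
- The Appendix F instruction to subjects to report a pregnancy is limited to the time on study.
- Section 7.5 requires sites to report pregnancies once they know of them. That helps only if the subject tells the site.

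None of these carries the 30 or 14 days.

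**The case against.** The best defence is that Section 1.4.1.2 is itself mandatory and adds to the other rules. Nothing in criteria 7 and 8 or Appendix F says contraception may stop before the 30 or 14 days are over, so a site reading the whole protocol would apply the longer period. On that view a cross-reference is missing and there is no contradiction. This is a fair description of the cause. It does not remove the effect, because subjects agree to the criteria and Appendix F, and those can be met in full while missing the longer period.

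The trial-level reading is the weaker one for a duty on an individual. It also covers everyone who finishes at least 30 days before the last visit. That is right, and the 365-day figure depends on that reading and on 12-month accrual. The gap does not need it, since the subject-level reading leaves a completer who doses to the visit with no cover.

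The practical size may be small. Section 1.1 describes a home-site population that is close to 80% male. If that held for all 60 subjects, about 60 × 0.20 = 12 would be women, and fewer of childbearing potential. A second site has since been added, so this is only indicative, and it does not count men with partners of childbearing potential. Appendix F says the non-clinical data raise no strong suspicion of harm to the fetus, and dosing after a reported pregnancy is left to clinical judgment. These points limit the severity; they do not supply the missing period.

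The consent form was not available. It may already state the 30 and 14 days, in which case subjects would have been told correctly despite the protocol text.

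**Conclusion.** The concern holds. The post-treatment period in Section 1.4.1.2 is not carried into any rule that subjects agree to, and neither meaning of end of study secures it.

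For a completer who doses up to the Week 48 visit, on the subject-level reading, the shortfall is the whole period: 30 days for women and 14 for men. If dosing stops at Day 336, cover runs from 0 to 28 days depending on a visit between Day 336 and Day 364. On the trial-level reading the shortfall falls on subjects who finish near the end of the trial.

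Subjects who stop drug early but stay on study through Week 48 (Section 3.2.4) may be covered on either reading. The last-dose days used above are assumptions, and the number of affected subjects cannot be derived. No known harm is claimed. The wording should be corrected, but the trial's conclusions do not depend on it.

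**What to change.** Amend inclusion criteria 7 and 8 (synopsis and Section 5.2) and both contraception requirements in Appendix F. They should run until at least 30 days after the subject's own last dose for women of childbearing potential, and at least 14 days for men with female partners of childbearing potential, or until the subject's own final study visit if that is later. Extend the Appendix F instruction to report a pregnancy, in the subject or a partner, to the same date. Align the consent form if it differs. The shortfall in required cover then becomes 0 days for every subject, and early completers are not bound until the last patient finishes.

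The cost is a wording amendment and possibly a consent update. Subjects accept a commitment up to 30 or 14 days longer than on the subject-level reading. No new visit is needed, but since none follows Week 48, detection in that period would rest on what subjects report. Deleting the 30 and 14 days from Section 1.4.1.2 would also make the text consistent, but it would lower protection and the protocol gives no reason for doing so.

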1.4.2 Risk of FibroScan® Test

FibroScan® is a noninvasive diagnostic ultrasound based device used to measure liver scarring, or fibrosis, caused by various diseases including HBV. It provides a non-surgical alternative to liver biopsy to assess liver damage.

In preparation for this procedure, subjects will be advised not to eat or drink (excluding water) for at least 3 hours prior to procedure. The FibroScan® test usually takes about 5-10 minutes. During the procedure, the subject will lie supine on his/her back with the right arm raised behind his/her head and the right abdominal area is exposed. A trained study staff member will apply a water-based gel to the skin and place the non-invasive probe over the liver area.

Fasting prior to procedure can result in hypoglycemia, lightheadedness or fainting. During the procedure, there is a small but possible risk of localized allergic reaction and irritation related to the water-based lubricating gel as well as discomfort due to positioning while in supine position.

1.4.3 Risk of Blood Draw

Collecting blood samples from a vein may cause pain, bruising, lightheadedness, fainting, bleeding and rarely infection at the site of the needle stick.

1.4.4 Risk of Electrocardiogram (ECG)

After an ECG, subjects may experience mild skin irritation, slight redness or itching where the recording patches were placed. They may also need to have chest hair shaved for the procedure.

1.4.5 Risk of Allergic Reactions

Allergic reaction is always possible with a drug that the study participant has never been exposed to before. Serious allergic reactions that can be life-threatening may occur. Some things that happen during any allergic reaction to any type of medication are: rash, difficulty breathing, wheezing, sudden drop in blood pressure, swelling around the mouth, throat, or eyes, fast pulse, and/or sweating may occur. Study participants will be monitored closely for any reactions.

